7.0 TRIAL PROCEDURES

7.1 Trial Procedures

The Trial Flow Chart - Section 6.0 summarizes the trial procedures to be performed at each visit. Individual trial procedures are described in detail below. It may be necessary to perform these procedures at unscheduled time points if deemed clinically necessary by the investigator.

Furthermore, additional evaluations/testing may be deemed necessary by the Sponsor and/or Merck for reasons related to subject safety. In some cases, such evaluation/testing may be potentially sensitive in nature (e.g., HIV, Hepatitis C, etc.), and thus local regulations may require that additional informed consent be obtained from the subject. In these cases, such evaluations/testing will be performed in accordance with those regulations.

7.1.1 Administrative Procedures

7.1.1.1 Informed Consent

The Investigator must obtain documented consent from each potential subject prior to participating in a clinical trial.f

7.1.1.2 Medical History

A medical history will be obtained by the investigator or qualified designee. Medical history will include all active conditions, and any condition diagnosed within the prior 10 years that are considered to be clinically significant by the Investigator. Details regarding the disease for which the subject has enrolled in this study will be recorded separately and not listed as medical history.

7.1.1.3 Concomitant Medications Review

7.1.1.3.1 Prior Medications

The investigator or qualified designee will review prior medication use, including any protocol-specified washout requirement, and record prior medication taken by the subject within 28 days before starting the trial. Treatment for the disease for which the subject has enrolled in this study will be recorded separately and not listed as a prior medication.

7.1.1.3.2 Concomitant Medications

The investigator or qualified designee will record medication, if any, taken by the subject during the trial. All medications related to reportable SAEs and ECIs should be recorded as defined in Section 7.2.

7.1.1.4 Disease Details and Treatments

7.1.1.4.1 Disease Details

The investigator or qualified designee will obtain prior and current details regarding disease status.

7.1.1.4.2 Prior Treatment Details

The investigator or qualified designee will review all prior cancer treatments including systemic treatments, radiation and surgeries.

7.1.1.4.3 Subsequent Anti-Cancer Therapy Status

The investigator or qualified designee will review all new anti-neoplastic therapy initiated after the last dose of trial treatment. If a subject initiates a new anti-cancer therapy within 30 days after the last dose of trial treatment, the 30 day Safety Follow-up visit must occur before the first dose of the new therapy. Once new anti-cancer therapy has been initiated the subject will move into survival follow-up.

7.1.1.5 Trial Compliance (Medication/Diet/Activity/Other)

Patients will be monitored for treatment compliance in addition to general compliance with clinic visits, prohibited activities, and concomitant medication. In the event that a patient is unwilling or unable to maintain compliance, then the patient can be removed from the study pending investigator and treating physician discretion.

7.1.2 Clinical Procedures/Assessments

7.1.2.1 Adverse Event (AE) Monitoring

The investigator or qualified designee will assess each subject to evaluate for potential new or worsening AEs as specified in the Trial Flow Chart and more frequently if clinically indicated. Adverse experiences will be graded and recorded throughout the study and during the follow-up period according to NCI CTCAE Version 4.0 (see Section 13.2). Toxicities will be characterized in terms regarding seriousness, causality, toxicity grading, and action taken with regard to trial treatment.

All AEs of unknown etiology associated with MK-3475 exposure should be evaluated to determine if it is possibly an event of clinical interest (ECI) of a potentially immunologic etiology (irAE). See Section 5.6.1.1 and the separate guidance document in the administrative binder regarding the identification, evaluation and management of AEs of a potential immunological etiology.

Please refer to section 7.2 for detailed information regarding the assessment and recording of AEs.

7.1.2.2 Directed Physical Exam

For cycles that do not require a full physical exam per the Trial Flow Chart, the investigator or qualified designee will perform a directed physical exam as clinically indicated prior to trial treatment administration.

7.1.2.3 Vital Signs

The investigator or qualified designee will take vital signs at screening, prior to the administration of each dose of trial treatment and at treatment discontinuation as specified in the Trial Flow Chart (Section 6.0). Vital signs should include temperature, pulse, respiratory rate, weight and blood pressure. Height will be measured at screening only.

7.1.2.4 Eastern Cooperative Oncology Group (ECOG) Performance Scale

The investigator or qualified designee will assess ECOG status (see Section 13.1) at screening, prior to the administration of each dose of trial treatment and discontinuation of trial treatment as specified in the Trial Flow Chart. After Cycle 8 assessment of ECOG status will be performed every other cycle in conjunction with the directed or full physical exam.

7.1.2.5 Tumor Imaging and Assessment of Disease

Response and progression will be evaluated in this study using guidelines proposed by the Immune Related Response Criteria (irRC). Patients with measurable disease will also be assessed using standard RECIST v 1.1 and World Health Organization (WHO) treatment response criteria.

7.1.2.5.1 irRC: Measurable Disease Prior to Therapy

Index lesions: Up to 15 index lesions per patient (5 per organ, up to 10 visceral and 5 cutaneous) with minimum size 5 x 5 mm will be accurately measured in two dimensions (two largest perpendicular diameters) on CT or MRI scan (slice thickness no greater than 5 mm) prior to therapy initiation. Lesions measured with calipers by clinical exam may be conducted on lesions no smaller than 10 mm in the smallest dimension. Lesions that cannot be accurately measured with calipers should be recorded as non-measurable.

XRT-treated index lesions: Defined as all index lesions treated by XRT as part of this protocol.

Non-XRT-treated index lesions: Defined as all index lesions not treated by XRT as part of this protocol.

irRC: Index and non-Index Lesions:

For the irRC, index and measurable new lesions are taken into account (in contrast to conventional WHO treatment response criteria, which do not require the measurement of new lesions, nor are new lesion measurements included in the assessment of evolving tumor

burden). At the baseline tumor assessment, the sum of the products of the two largest perpendicular diameters (SPD) of all index lesions (five lesions per organ, up to 10 visceral lesions and five cutaneous index lesions) is calculated. At each subsequent tumor assessment, the SPD of the index lesions and of new, measurable lesions ($\geq 5 \times 5$ mm; up to 5 new lesions per organ: 5 new cutaneous lesions and 10 new visceral lesions) are added together to provide the total tumor burden. In addition to a global irRC which will encompass all lesions under the previous definition, the irRC of lesions included within the XRT PTV and outside the XRT PTV will also be assessed as follows:

1. **Global irRC:** irRC that factors all lesions including both index and non-index as outlined in 9.2.4.
2. **In-Field irRC:** irRC in which only index within the XRT PTV will be considered and any non-index lesions arising inside the XRT PTV
3. **Out-Field irRC:** irRC in which only index lesions outside the XRT PTV will be considered and any non-index lesions arising outside the XRT PTV

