2.2 Trial Diagram

- For Part A we will allow induction chemotherapy
- Primary Endpoint
 - Safety
- Secondary endpoint
 - Improvement in PFS compared to historical controls

[figure not shown]
Part A: Is only for patients with Limited Stage SCLC, we will allow induction chemotherapy. The total cycles of chemotherapy recommended will be 4, as such if a patient had two cycles of induction chemotherapy they would only get an additional two with MK-3475. PCI will be allowed based on the treating physician discretion and will be done after chemotherapy has been completed. PCI will delay the next dose of MK-3475 by one cycle and PCI should start approximately three weeks after MK-3475. MK-3475 can be resumed following the completion of PCI. LS-SCLC patients, who achieve systemic disease control during/after completion of 16 cycles of MK-3475, will be eligible to get additional 16 cycles of MK-3475, provided they did not exhibit severe (grade >3) MK-3475 related toxicity during therapy. Systemic disease control is defined as stable disease or partial response or complete response, based on irRC criteria.

Part A for LS-SCLC

* Eligible patients may receive additional 16 cycles.

Part B: Is only for patients with Extensive Stage SCLC who are receiving consolidation XRT after 1-6 cycles of chemotherapy. Patients needing PCI are encouraged to have it completed prior to enrollment in this trial. If PCI needs to be given on study, after thoracic XRT, then it should be done in a manner consistent with part A. PCI will delay the next dose of MK-3475 by one cycle and PCI should start approximately three weeks after MK-3475. MK-3475 can be resumed following the completion of PCI.) Patients needing XRT treatment to other sites outside the thorax will be allowed, but is encouraged to be done prior to starting the trial.

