4.2.2 Rationale for Dose Selection/Regimen/Modification

Radiation for limited stage disease will be administered at the standard doses of 45Gy in twice daily fractions, with concurrent chemotherapy, either cisplatin and etoposide or carboplatin and etoposide. Patients with extensive stage disease will receive thoracic radiation to 45 Gy in daily fractions, without concurrent chemotherapy. While on study, patients are allowed to have further radiation to other clinically appropriate sites as per the discretion of their treating radiation oncologist.

MK-3475: Will be started at 100 mg, 1/2 the MTD of MK-3475 alone (based on MTD dose of 200mg Q 3 weeks). The dose will be changed as per our 3x3 dose escalation rules and either decreased to 70mg, continued at 100m or increased to 150mg and eventually 200mg.

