5.1.3 Subject Exclusion Criteria

The subject must be excluded from participating in the trial if the subject:

1. Is currently participating in or has participated in a study of an investigational agent (except glutamine) or using an investigational device within 2 weeks of the first dose of treatment.
2. Has a diagnosis of immunodeficiency or is receiving systemic steroid therapy or any other form of immunosuppressive therapy within 7 days prior to the first dose of trial treatment. With the exception of physiologic steroid replacement.
3. Has had a prior monoclonal antibody within 2 weeks prior to study Day 1 or who has not recovered (i.e., \leq Grade 1 or at baseline) from adverse events due to agents administered more than 4 weeks earlier.
4. Has had prior chemotherapy, targeted small molecule therapy, within 2 weeks prior to study Day 1 or who has not recovered (i.e., \leq Grade 1 or at baseline) from adverse events due to a previously administered agent. Prior radiation does not require a washout period.
 - Note: Subjects with \leq Grade 2 neuropathy are an exception to this criterion and may qualify for the study.
 - Note: If subject received major surgery, they must have recovered adequately from the toxicity and/or complications from the intervention prior to starting therapy.
5. Has a known additional malignancy that is progressing or requires active treatment. Exceptions include basal cell carcinoma of the skin, squamous cell carcinoma of the skin, or in situ cervical cancer that has undergone potentially curative therapy.
6. Has known active central nervous system (CNS) metastases and/or carcinomatous meningitis. Subjects with previously treated brain metastases may participate provided they are stable (without evidence of progression by imaging for at least four weeks prior to the first dose of trial treatment and any neurologic symptoms have returned to baseline), have no evidence of new or enlarging brain metastases, and are not using steroids for at least 7 days prior to trial treatment.

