5.2.1 Dose Selection/Modification

5.2.1.1 Dose Selection

The rationale for selection of doses to be used in this trial is provided in Section 4.0 – Background and Rationale.

The dose amount required to prepare the MK-3475 infusion solution will be based on the dose level which a patient is being treated on as per table 1.

Radiation will be given as per our institutional standard. For the patient in the LS-SCLC arm we will use 45Gy delivered BID over 15 days (we will allow a GTV boost to 54Gy, as long as the PTV dose remains at 45Gy). For patients with ES-SCLC we will use a dose of 45Gy daily (we will allow at GTV boost dose to 52.5Gy, as long as the PTV dose remains at 45Gy).

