7.1.2.5.2 Guidelines for Evaluation of Measurable Disease

All measurements should be taken and recorded in metric notation using a ruler or physical calipers. All baseline evaluation studies should be performed as closely as possible to the beginning of treatment and never more than 4 weeks before the beginning of treatment. The same method of assessment and the same technique should be used to characterize each identified and reported lesion at baseline and during follow-up. Imaging-based evaluation is preferred to evaluation by clinical examination when both methods have been used to assess the antitumor effect of a treatment.

Clinical lesions. Clinical lesions will only be considered measurable when they are superficial (e.g., skin nodules and palpable lymph nodes). In the case of skin lesions, documentation by color photography, including a ruler to estimate the size of the lesion, is recommended.

Chest x-ray. Lesions on chest X-ray are acceptable as measurable lesions when they are clearly defined and surrounded by aerated lung. However, cross sectional imaging is preferable.

Multidetector CT, PET/CT. These techniques should be performed with contiguous slices of 5 mm or less in thickness. This applies to tumors of the neck, chest, abdomen and pelvis. Head and neck tumors and those of extremities may require specific imaging protocols or evaluation with ultrasound. When the primary endpoint of the study is objective response evaluation, US should not be used to measure tumor lesions. It is, however, a possible alternative to clinical measurements of superficial palpable lymph nodes, subcutaneous lesions, and thyroid nodules. US might also be useful to confirm the complete disappearance of superficial lesions usually assessed by clinical examination.

Endoscopy, Laparoscopy. These will not be used to assess response on this study.

Tumor markers. Tumor markers alone cannot be used to assess response. If markers are initially above the upper normal limit, they must normalize for a patient to be considered in complete clinical response.

Cytology, Histology. These techniques can be used to differentiate between partial responses (PR) and complete responses (CR) if clinically indicated.

7.1.2.5.3 Immune Related Response Criteria (irRC).

Evaluation of Target Lesions

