Response in new patients will be conducted using the Immune Related Response Criteria (irRC) as described in¹⁰. “For irRC, only index and measurable new lesions are taken into account. At the baseline tumor assessment, the sum of the products of the two largest perpendicular diameters (SPD) of all index lesions (five lesions per organ, up to 10 visceral lesions and five cutaneous index lesions) is calculated. At each subsequent tumor assessment, the SPD of the index lesions and of new, measurable lesions ($\geq 5 \times 5$ mm; up to 5 new lesions per organ: 5 new cutaneous lesions and 10 visceral lesions) are added together to provide the total tumor burden:”

For the purposes of this study, 3 separate tumor burdens will be calculated for each patient and used to define 3 separate irRCs as discussed in 9.3. All criteria will be considered separately for all 3 irRCs: global, in-field, and out-field.

Global Tumor Burden = SPD(all index lesions) + SPD(new, measurable lesions)

In-Field Tumor Burden = SPD(all index lesions targeted by XRT in this protocol) + SPD(new, measurable lesions inside the XRT PTV)

Out-Field Tumor Burden = SPD(all index lesions NOT targeted by XRT in this protocol) + SPD(new, measurable lesions outside the XRT PTV)

Complete Response (irCR): irCR, complete disappearance of all lesions (whether measurable or not, and no new lesions) confirmation by a repeat, consecutive assessment no less than 4 wk from the date first documented.

Partial Response (irPR): irPR, decrease in tumor burden $\geq 50\%$ relative to baseline confirmed by a consecutive assessment at least 4 wk after first documentation.

Progressive Disease (irPD): irPD, increase in tumor burden $\geq 25\%$ relative to nadir (minimum recorded tumor burden) confirmation by a repeat, consecutive assessment no less than 4 wk from the date first documented.

1. If a patient is classified as having irPD at a post-baseline tumor assessment, then confirmation of irPD by a second scan in the absence of rapid clinical deterioration is required. The definition of confirmation of progression represents an increase in tumor burden $\geq 25\%$ compared with the nadir at two consecutive time points at least 4 wk apart. It is recommended that this be done at the discretion of the investigator

because follow-up with observation alone may not be appropriate for patients with a rapid decline in performance status.

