All recorded adverse events will be recorded per MDACC guidelines using CTCAE Version 4.0. Frequency of adverse events will be tabulated by grade, type, and dose/cohort. Relative frequencies and confidence intervals will also be constructed.

9.2.4. *Efficacy Analyses*

Efficacy data from part A and part B will be performed using the criteria below.

1. **Global irRC:** irRC that factors all lesions both index and non-index.
2. **In-Field irRC:** irRC in which only XRT-treated lesions will be considered and non-index lesions arising inside the XRT PTV
3. **Out-Field irRC:** irRC in which only non XRT-treated lesions will be considered and non-index lesions arising outside the XRT PTV

Time-to-event distributions for PFS and OS will be estimated via Kaplan-Meier analysis. Summary statistics will be computed along with confidence intervals. The limited sample size precludes formal statistical comparison with historical controls.

9.2.5. *Sample Size/Accrual Rate*

The maximum planned number of patients will be 80, with 40 patients being treated with LS-SCLC and 40 patients with ES-SCLC. It is estimated that approximately 1.5 patients per month (for both LS-SCLC and ES-SCLC) will be accrued over 26 months. With 40 patients, the probability of seeing at least one patient with toxicity if the true toxicity rate is 0.1 is 88%. The 95% binomial confidence interval for 6/20 (30%) extends from 15% to 52%.

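### Out-field irRC can include lesions irradiated before entry, and the field-specific irRCs do not say how to count patients with no baseline lesion in that field

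*Combined protocol and SAP*

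**What the plan says.** **Which lesions are out-field.** Section 7.1.2.5.1 gives the definition: "Non-XRT-treated index lesions: Defined as all index lesions not treated by XRT as part of this protocol". The list of three irRCs in the same section uses position relative to the XRT PTV instead. The formula in section 7.1.2.5.3 begins "Out-Field Tumor Burden = SPD(all index lesions NOT targeted by XRT in this protocol" and adds new measurable lesions outside the PTV. Section 9.2.4 describes the out-field criterion as "irRC in which only non XRT-treated lesions will be considered and non-index lesions arising outside the XRT PTV".

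**Radiation outside the trial field.** Section 5.1.3, item 4, states: "Prior radiation does not require a washout period". In the Part B paragraph of section 2.2: "Patients needing XRT treatment to other sites outside the thorax will be allowed, but is encouraged to be done prior to starting the trial". For the on-study period, section 4.2.2 says that "patients are allowed to have further radiation to other clinically appropriate sites as per the discretion of their treating radiation oncologist". Section 7.1.2.5.2 requires baseline studies as near to treatment as possible and "never more than 4 weeks before the beginning of treatment".

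**Who is counted.** Section 9.1 makes anyone given any MK-3475 evaluable for response. Section 7.1.2.5.3 calculates global, in-field and out-field burdens for each patient and applies all criteria to each. Section 5.1.2, item 3, recognises that some patients may have no measurable disease after induction. irPR is a fall of at least 50% from baseline, and irPD a rise of at least 25% from nadir. irSD is what remains when neither response nor irPD applies.

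**The concern.** The rationale in section 4.2.1 is that radiation primes a systemic (abscopal) response. Of the three imaging criteria, the out-field irRC is, by inference, the one closest to that idea. Two features blur it.

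First, a lesion irradiated shortly before entry may still be shrinking from that radiation after the baseline scan. The plan would score the shrinkage as change outside the field. It could offset real growth in a never-irradiated lesion or, less easily, produce an irPR.

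Second, a patient with no baseline lesion in a field has nothing there that can respond, yet belongs to the evaluable set. The field response rate then depends on an unstated convention for that patient, and the convention can move the rate in either direction.

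**Working it through.** The plan gives no response rate, power or sample size for the field-specific irRCs, so there is no figure to reproduce. The check is of the wording, followed by illustrations. Lesion sizes, the share of empty fields and the 10% rate are assumptions; n = 40 per part is from section 9.2.5.

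**1. Where a lesion irradiated before entry, outside the thoracic PTV, falls**

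| Place | Sorted by | Class |
|---|---|---|
| 7.1.2.5.1, definition | treated by this trial's XRT | out-field |
| 7.1.2.5.1, list of irRCs | position relative to PTV | out-field |
| 7.1.2.5.3, formula | targeted by this trial's XRT | out-field |
| 9.2.4 | XRT-treated or not, source of XRT not stated | out-field if the 7.1.2.5.1 term is meant; excluded if read literally |

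For on-study radiation to another site, no section says whether it counts as protocol XRT. If it does not, the lesion stays out-field while being irradiated. If it does, the lesion belongs with the treated ones.

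**2. Masking of growth.** Let s be the irradiated share of the out-field baseline burden, g the growth of the rest and d the shrinkage of the irradiated part. Then change = (1 − s)g − s·d. At the first scan after baseline, nadir = baseline. Take two lesions of 4 cm² each, so s = 0.5.

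- g = 50%, d = 0: (4 + 6)/8 − 1 = +25%, irPD size.
- g = 50%, d = 10%: (3.6 + 6)/8 − 1 = +20%, irSD.
- g = 50%, d = 100%: (0 + 6)/8 − 1 = −25%, irSD.
- g = 75%: 37.5% − 0.5d, below 25% when d exceeds 25%.
- g = 100%: 50% − 0.5d, below 25% when d exceeds 50%.

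**3. Spurious irPR.** With the other lesions unchanged (g = 0), irPR needs s × d ≥ 0.50. The shrinkage required is 0.50/0.50 = 100% at a 50% share, 0.50/0.667 = 75% at a 67% share and 0.50/0.80 = 62.5% at an 80% share, confirmed at least 4 weeks later. This is a much higher bar than masking.

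**4. Classifying an empty field.** With a baseline burden of 0, the irPR percentage is 0/0. If no new lesion appears there is no increase, so irPD is absent and the patient falls to irSD by default. A reader could instead assign irCR, because no lesion is present. If a new measurable lesion appears, the burden rises from 0: any increase exceeds 25% of 0, but the percentage itself has no value.

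**5. Effect on the rate.** Assume a 10% out-field response rate among patients with an out-field baseline lesion.

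| Assumed share without a lesion | Patients with a lesion | Empty fields left out | Counted as non-responders | Counted as irCR |
|---|---|---|---|---|
| 25% | 30 | 3/30 = 10% | 3/40 = 7.5% | (3 + 10)/40 = 32.5% |
| 50% | 20 | 2/20 = 10% | 2/40 = 5% | (2 + 20)/40 = 55% |
| 75% | 10 | 1/10 = 10% | 1/40 = 2.5% | (1 + 30)/40 = 77.5% |

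Under the irSD reading, 10, 20 or 30 of the 40 patients would be listed as stable in a field where they had no lesion.

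**The case against.** Sorting lesions by the trial's own field is a legitimate contrast, and sections 7.1.2.5.1 and 7.1.2.5.3 apply it consistently. They do not call out-field lesions non-irradiated; section 3.3 uses that term, but for T-cell changes. This stands as a defence of the wording. It does not prevent direct radiation effect from entering the out-field result.

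Section 5.2.1.1 sets out the trial's radiation and its PTV dose (for ES-SCLC, "we will allow at GTV boost dose to 52.5Gy, as long as the PTV dose remains at 45Gy"), and section 4.2.2 leaves other sites to the treating radiation oncologist. The natural reading is that such radiation is not protocol XRT. That is fair, but it leaves an irradiated lesion in the out-field sum, so the rule still needs stating.

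The encouragement to irradiate other sites before entry is in the Part B paragraph, so the first problem falls mainly there; the absence of a washout applies to both parts. A baseline scan close to treatment limits carry-over, and the masking example at 50% growth sits exactly on the 25% threshold. Both points stand.

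A reader might infer that an empty field cannot be classified at all, or that empty fields necessarily dilute the rate. Neither follows. Absence of irPD is clear when no new lesion appears, and the irCR reading inflates the rate instead. Nor is evaluability unaddressed: section 9.1 has a general rule, but it says nothing about individual fields. Section 9.2.4 specifies no field-specific denominator, so using the section 9.1 set is the direct reading, not an explicit instruction. The irRC is also applied by citation, and what the cited source says on these points cannot be judged from the documents.

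**Conclusion.** The point holds as a modest one. As written, a lesion irradiated before entry is an out-field index lesion under sections 7.1.2.5.1 and 7.1.2.5.3, while section 9.2.4 can be read either way. The status of on-study radiation to other sites is not stated. Patients with no baseline lesion in a field enter its summary without a defined irPR percentage. They become irSD by default or could be read as irCR.

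Under the assumptions above, a little residual shrinkage can hide growth near the irPD threshold, whereas a spurious irPR needs 62.5% to 100% shrinkage at shares of 80% down to 50%. With half the fields empty, a 10% rate could be reported as 5% or 55%. The documents give no lesion mix and no frequency of empty fields, so these figures show direction and possible size, not expected bias.

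A reader might infer that the trial's efficacy or dose conclusions are compromised. The documents do not support that. Section 9.2.1 makes these summaries descriptive, out-field response is not among the objectives in section 3, and dose finding rests on toxicity.

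**What to change.** Change the scoring text only; which radiation is allowed is unaffected.

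- In sections 7.1.2.5.1, 7.1.2.5.3 and 9.2.4, use one definition: out-field index lesions lie outside the protocol thoracic PTV and had no radiation before baseline.
- Keep lesions outside the PTV that were irradiated before entry in the global burden, and list them separately.
- If an out-field lesion is irradiated on study, drop it from the out-field baseline, nadir and follow-up sums alike from that date, so that its removal is not read as shrinkage. Confirmed classifications already recorded stand; unconfirmed ones are reported as unconfirmed.
- Report in-field and out-field response among patients with a baseline lesion in that field. Show the others as *no baseline lesion in field*, and report any new lesion there as progression in that field.
- Leave the global irRC on the section 9.1 denominator.

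**Cost.** Section 7.1.1.4.2 already has prior radiation reviewed, but not lesion by lesion, and the flow chart in section 6.1 has no item for on-study radiation to other sites. Site and date would have to be recorded per lesion for both. Field denominators become smaller and intervals wider: 2/20 has an exact (Clopper-Pearson) 95% interval of 1.2% to 31.7%, against 0.6% to 16.9% for 2/40.
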